Study Biostatistician:	NAME Clinical Trial Consultants CTC AB [name] Telephone: TELEPHONE Email: NAME
Pharmacovigilance:	CTC Pharmacovigilance Department Email: [contact]

Electronic case report form
(eCRF) and patient reported
outcomes (ePRO) system
provider:

Viedoc Technologies AB
[name]
SE-753 40 Uppsala, Sweden
Email: [contact]

APPROVAL PAGE

Sponsor:

NAME, Gedea Biotech AB

Date:

Coordinating Investigator:

NAME
Danderyds sjukhus

Date:

Biostatistician:

NAME
Clinical Trial Consultants CTC AB

Date:

SYNOPSIS

Name of Sponsor: Gedea Biotech AB
Name of product: Gedea Pessary (p Hyph gen II)
Name of active ingredient: Glucono-delta-lactone (GDL) and sodium gluconate (NaG).
Title of study: An open-labelled study to evaluate clinical performance of the Gedea Pessary in adult women with vulvovaginal candidiasis
Clinical investigation plan number: QRS-CL4-003
Coordinating Investigator: NAME
Classification of study: Clinical investigation
Objectives: Primary objective: To investigate the clinical performance of acute treatment with Gedea Pessary in patients with vulvovaginal candidiasis (VVC). Primary endpoint: Clinical cure rate on Day 7-14, defined as the percentage of patients clinically cured at Day 7-14. Secondary objectives: To investigate the safety of acute treatment with Gedea Pessary and to further investigate the clinical performance of acute treatment with Gedea Pessary in patients with VVC. Secondary endpoints: 
1. Safety and tolerability, based on reported treatment-emergent adverse events (AEs) (safety endpoint).2. Proportion of patients having a continued clinical response to treatment at Day 25, defined as the proportion of patients clinically cured on Day 7-14 and thereafter responding "no" to the yes/no question, "Have the symptoms recurred?"3. Proportion of patients having a cure defined as clinical cure Day 7-14 according to primary endpoint and mycological cure (culture negative for growth of Candida species).4. Proportion of patients having a reduction in composite vulvovaginal signs and symptoms (CVVS) score on Day 7-14 compared to Day 0.5. Change in the CVVS score from Day 0 to Day 7-14.

6. Proportion of patients having a reduction in the sum of the 3 vulvovaginal symptoms scores (itching, burning, and irritation) on Days 1-7, Day 11, Day 14 and Day 25, compared to Day 0.
7. Change in the sum of the 3 vulvovaginal symptoms scores (itching, burning, and irritation) on Days 1-7, Day 11, Day 14 and Day 25, compared to Day 0.
8. Proportion of patients having a mycological cure as assessed by vaginal culture on Day 7-14 and Day 25.
9. Proportion of patients having an absence of Candida hyphae in the wet smear on Day 7-14.
10. Usability, measured by patient questionnaire, on Day 6.

Exploratory endpoints:

1. Correlation between vaginal microbiome as assessed by vaginal swab DNA-analysis on Days 0, 7, 14, and 25 and clinical cure.
2. Correlation of presence of fungus as analysed by vaginal swab DNA-analysis on Days 0, 7, 14 and 25 and presence of fungus as assessed by culture, and clinical cure.

Methodology:

This is an open-labelled study to evaluate the clinical performance and safety of treatment with Gedea Pessary in adult women with confirmed VVC.

Number of patients planned:

26 patients

Diagnosis and main criteria for inclusion:

The study population will consist of post-menarchal, pre-menopausal females, 18 years or older, seeking care for VVC symptoms. To be included in the study, patients should have a VVC diagnosis. Patients with known or apparent signs of other infectious causes of VVC and patients who were treated for VVC within the past 14 days, or are currently receiving anti-fungal therapy unrelated to VVC will be excluded from the study.

Investigational products, dose and mode of administration:

Test product: Gedea Pessary, a pessary containing 150 mg GDL and 184 mg NaG, administered vaginally with a CE-marked pessary applicator. The Gedea Pessary (commercial name *pHyph*) is a Class IIb medical device according to Medical device regulation (MDR) 2017/745.

Study duration:

Planned study time: First patient in: Q1 2023. Last patient out: Q3 2023.

Duration: Patients will be treated for 6 days (Day 0 to Day 5) and have 4 follow-ups (on Day 4, Day 7, Day 14 and Day 25). The total study duration will be 26 days (± 3 days), including Screening.

Statistical methods:

Assuming a true proportion of 54% clinically cured in the treated group a sample size of 24 patients is needed to obtain 80% power to show that the one-sided 95% confidence interval (CI) for the clinical cure rate is above 30%. To compensate for patients with missing data a total of 26 patients will be included.

The primary performance objective of the trial is to show that the clinical cure rate is above 30 %, i.e. to show that the one-sided 95 % CI for the observed cure rate is above 30 %. The primary

endpoint, clinical cure rate on Day 7-14, will be presented together with a one-sided 95% CI based on the Wilson score.

The secondary endpoint safety and tolerability, based on reported treatment-emergent adverse events (AEs) will be presented descriptively.

All secondary clinical performance endpoints will be presented with descriptive statistics. Binary secondary clinical performance endpoints will show the endpoint estimate together with a two-sided 95% CI based on the Wilson score. Presentation of continuous secondary clinical performance endpoints will include the two-sided 95% CIs for the arithmetic mean.

TABLE OF CONTENTS

INVESTIGATORS AND STUDY ADMINISTRATIVE STRUCTURE	2
APPROVAL PAGE.....	4
SYNOPSIS	5
TABLE OF CONTENTS.....	8
LIST OF FIGURES	10
LIST OF TABLES	11
LIST OF APPENDICES.....	11
LIST OF ABBREVIATIONS.....	12
1 STATEMENT OF COMPLIANCE	14
2 ETHICAL AND REGULATORY CONSIDERATIONS	14
3 INTRODUCTION.....	15
3.1 Indication.....	15
3.2 Glucono-delta-lactone, mode of action	16
3.2.1 Biofilm	16
3.2.2 Lactobacilli	17
3.3 Product description and previous experience	17
3.3.1 Non-clinical data.....	17
3.3.2 Clinical data	18
4 STUDY OBJECTIVES.....	20
4.1 Primary objective	20
4.1.1 Primary endpoint.....	20
4.2 Secondary objectives.....	21
4.2.1 Secondary endpoints	21
4.3 Exploratory objectives.....	21
4.3.1 Exploratory endpoints	21
5 STUDY DESIGN.....	22
5.1 General outline	22
5.2 Rationale for the study design	26
5.3 Risks and benefits.....	27
5.4 Study visits and procedures.....	28
5.4.1 Day 0; Screening and enrolment.....	28
5.4.2 Day 0 to Day 5; Treatment administration.....	29
5.4.3 Day 7 (+2 days); Follow-up visit	29
5.4.4 Day 11 (± 1 day); Follow-up at home	30
5.4.5 Day 14 (± 2 days); Follow-up visit	30
5.4.6 Day 25 (± 2 days); Follow-up visit	31
5.4.7 Early withdrawal visit	32
6 SELECTION OF STUDY POPULATION.....	32
6.1 Patient information and informed consent	32
6.2 Recruitment	33
6.3 Inclusion criteria.....	33
6.4 Exclusion criteria.....	34
6.5 Restrictions.....	34
6.6 Withdrawal of patients and termination of the investigation	34

6.6.1	Withdrawal from study and termination criteria	34
6.6.2	Reasons for treatment discontinuation or withdrawal from the study	35
6.6.3	Procedure for withdrawal of a patient.....	35

SaaS	Software as a Service
SADE	Serious adverse device effect
SAE	Serious adverse event
SAP	Statistical analysis plan
SAS	Statistical analysis software
SOC	System organ class
SOP	Standard operating procedure
VVC	Vulvovaginal candidiasis
U-HCG	Urinary human chorionic gonadotropin
USADE	Unanticipated serious adverse device effect
WHO	World Health Organization

1 STATEMENT OF COMPLIANCE

This clinical investigation will be conducted in accordance with this CIP which has been prepared in accordance with:

- The International Conference on Harmonisation (ICH) Guideline for Good Clinical Practice (GCP) (ICH Harmonised Tripartite Guideline)/Note for Guidance on Good Clinical Practice: CPMP/ICH/135/95, January 1997 (where applicable to medical devices).
- The principles of the European Standard EN International Organization for Standardization (ISO) 14155:2020 Clinical Investigation of Medical Devices for Human Patients – Good Clinical Practice.
- The Medical device regulation (MDR) 2017/745.
- MDCG 2020-10/1 Guidance on safety reporting in clinical investigations (May 2020)
- The latest revision of the Ethical Principles for Medical Research Involving Human Subjects (World Medical Association Declaration of Helsinki).
- The ICH E9 (R1) addendum: Statistical Principles for Clinical Trials.
- Local laws and regulations/applicable regulatory requirements.

2 ETHICAL AND REGULATORY CONSIDERATIONS

The Sponsor or designee will, prior to site initiation, obtain favourable opinion/approval to conduct the study from all regulatory agencies (RAs)/competent authorities (CAs) in accordance with any applicable country specific regulatory requirements.

It is the responsibility of the Sponsor to submit the CIP, any protocol amendments, the patient information sheet and informed consent form (ICF), patient recruitment procedures, the Investigator's Brochure (IB), information on payments and compensation available to patients, Investigator remuneration and other study-specific documentation (as required) to the applicable independent ethics committee (IEC).

Any additional requirements imposed by the IEC, RA or CA after their review shall be followed, as applicable.

The IEC which reviewed and approved the study, as well as the name of the committee chairmen will be included in the Clinical investigation report (CIR). All applicable ethical and regulatory approvals must be available before a patient is exposed to any trial-related procedure, including screening for eligibility.

The Coordinating Investigator is obliged to submit substantial amendments and other relevant updates to safety information to the IEC. The Sponsor is obliged to submit substantial amendments and other relevant documents to the RA.

No substantial amendments to the CIP may be implemented prior to receipt of written approval from the IEC and/or RA, as applicable, unless the amendments are necessary to avoid immediate hazard for the patient. The Coordinating Investigator will maintain an accurate and complete record of all submissions made to the IEC.

The Sponsor will compensate the study site for their work in the study. However, the compensation will not be affected by the outcome of the study.

Patients will receive a small token of appreciation as compensation for study participation and they will be reimbursed for any reasonable travel cost as a result of participating in this study.

All patients participating in the study can retrieve financial compensation in the case of harm (see [Section 13.10](#)).

Each patient will be given full information about the study and will be asked to sign the ICF prior to initiation of any study-related activities (see [Section 6.1](#)). Patients will be free to withdraw from the study at any time (see [Section 6.6.1](#)).

Each patient should be informed in writing that the study results will be stored and analysed in a computer, maintaining confidentiality in accordance with local data protection laws (see [Sections 6.1](#) and [13.9](#)).

3 INTRODUCTION

3.1 Indication

Vaginal infection is a huge and largely underestimated problem, affecting 70% to 75% of women at some point in their life, and 5% to 8% of adult women have recurrent vulvovaginal candidiasis (VVC) with ≥ 4 episodes yearly.^{1,2}

The vaginal microbiome is a dynamic system, composed of a complex mixture of microorganisms in different ratios and quantities, which depend on lactic acid producing bacteria to maintain a weakly acidic environment.³ Changes to vaginal microflora increase the pH, thereby forming a favourable environment for vaginal pathogens. Vaginal or systemic antibiotics treatment is frequently followed by VVC, likely due to the elimination of the protective bacterial flora, thereby allowing *Candida* overgrowth.⁴⁻⁸ Infections are also facilitated due to the mucosal effect of increased oestrogen levels and a weakened immune system during pregnancy.⁹ Recurrences are more common in pregnant women, and their therapeutic response is reduced compared to non-pregnant women.^{10,11} Further, contraceptive pills, menstruation, and diabetes mellitus have been identified as predisposing factors for VVC.^{12,13} *Candida albicans* is the most prevalent pathogen, which, according to epidemiological studies, is present in between 73% and 92% of vaginal isolations.¹⁴ *Candida glabrata* is the second most prevalent pathogen.¹⁴

Many women diagnose themselves with VVC and purchase over the counter (OTC) anti-mycotic treatments. However, many misdiagnose themselves and therefore receive unnecessary or inappropriate treatment.¹⁵ In a study of 95 symptomatic women who purchased OTC anti-mycotics for treatment of presumed VVC, only 34% of them were actually diagnosed with VVC.¹⁶ The most common other diagnoses were bacterial vaginosis (BV; 18.9%), mix of BV and VVC (18.9%), and normal (13.7%).

Current treatment strategies for uncomplicated or acute VVC include anti-mycotic vaginal creams or pessaries/vaginal tablets, such as econazole, clotrimazole, or miconazole for 1 to 7 days, or single-dose oral fluconazole. Reported clinical cure rates are variable, which may reflect different clinical cure definitions between studies. Clinical cure rates after 27 to 38 days of intravaginal imidazole treatment (clotrimazole, terconazole, butoconazole, or

miconazole) have been reported in a range of 64% to 87%, across different studies. None of these clinical cure rates were statistically significant.^{17, 18} Short-term clinical cure rates have been reported to be 85% 1 to 2 weeks after treatment,²⁰ but also as low as 35% 7 days after treatment.¹⁹ Mycological cure rates have been reported to be higher compared to clinical cure rates in some studies and lower in others.¹⁹⁻²²

Severe VVC is characterised by extensive vulvar oedema, excoriations, and fissure formation. Short courses of treatment, which are normally effective in uncomplicated VVC, are often not sufficient.¹⁵ Recommendations for treating severe and complicated VVC include 2 to 3 oral doses of fluconazole, oral itraconazole for 3 days, boric acid vaginal insert for 2 weeks, or topical therapy for 7 to 14 days.^{18, 22, 23}

Recurrent VVC is characterised by ≥ 4 yearly episodes, and treatment usually entails intensive initial therapy to induce clinical and mycological remission, followed by a 6-month systemic fluconazole maintenance therapy.^{15, 24, 25} While treatment guidelines for recurrent VVC are consistent, recommended treatments are not particularly effective in the long term^{17, 24}, as 30% to 50% of patients experience recurrence after treatment discontinuation.¹⁵

Oral anti-fungal therapies are not recommended during pregnancy due to the potential risk of foetal harm and spontaneous abortions.²⁶⁻²⁸ Therefore, treatment guidelines recommend that topical, rather than oral, anti-fungal therapy is used in pregnant women.¹⁷

There are limited data regarding the anti-fungal susceptibility of the *Candida* causing VVC, as VVC cultures are rarely performed. The prevalence of fluconazole-resistance among *C. albicans* isolates has been reported to be between 2.1% and 21% in different studies.³¹⁻³⁴ Fluconazole or itraconazole resistance is found in a larger proportion of non-albicans *Candida* species; resistance to fluconazole was found in 15% of *C. glabrata* isolates and 42% of *Candida krusei* isolates, and resistance to itraconazole was found in 74% and 58% of *C. glabrata* and *C. krusei* isolates, respectively.³³

In summary, current treatment and prevention strategies for infections in the genital area are limited, and there is a need for novel OTC treatment alternatives which are safe during pregnancy and have low risk for resistance development.

Given the high frequency of women misdiagnosing themselves with VVC, and self-treating with OTC treatments for VVC even though they in fact have a BV infection or mixed VVC and BV infection¹⁶, there is a need for products that are able to treat both VVC and BV.

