5.4.1 Day 0; Screening and enrolment

Patients seeking treatment for symptoms relating to VVC may be informed about the study and, if agree to participate, sign the ICF. After the ICF is signed, patients will undergo a gynaecological examinations, where the Investigator or an authorised designee will assess the presence of vulvovaginal signs (erythema, oedema, or excoriation) and symptoms (itching, burning, or irritation) and score each sign and symptom, as described in [Section 9.1](#).

Vaginal samples will be examined under a microscope for yeast forms (hyphae or pseudohyphae) or budding yeast. Two vaginal secretion samples will also be collected by a vaginal swab. One sample will be cultured to verify the presence of *Candida* and the other (taken in duplicates) will be used for sequencing analysis of the vaginal microbiome prior to treatment ([Section 10.1.1](#)). If the Investigator assesses that the patient has VVC, based on the gynaecological examination and the fungal microscopy, the patient will receive the investigational product to be self-inserted vaginally at home during 6 consecutive days (Days 0 to 5). In addition, the Investigator will measure the vaginal pH, as described in [Section 10.1.2](#).

The Investigator or delegatee will ask the patient about onset and end of last menstruation. The patient should not be enrolled, or the enrolment should be postponed, if menstruation is foreseen to occur at the time of the Day 7 visit.

Procedures to be performed:

- Informed consent
- Demography
- Eligibility criteria
- Pregnancy test (urinary)
- Recording of
 - Medical and surgical history
 - Prior and concomitant medications
 - Onset and end of last menstruation
- Gynaecological examination by Investigator or authorised designee, evaluating vulvovaginal signs (erythema, oedema, and excoriation) and symptoms (itching, burning, and irritation) according to a scoring scale (0-3).
- Fungal microscopy assessment (KOH or saline preparation)
- Vaginal swab for:
 - Culture
 - Sequencing
- Vaginal pH
- Treatment dispensing for self-administration by patients at home.

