5.4.3 Day 7 (+2 days); Follow-up visit

Patients will visit the clinic on Day 7 to have gynaecological examination performed. The Investigator or an authorised designee will assess the presence of vulvovaginal signs (erythema, oedema, and excoriation) and symptoms (itching, burning, and irritation) and score each sign and symptom on a scale of 0 to 3 (see [Section 9.1.2](#)).

Vaginal samples will be examined under a microscope for yeast forms (hyphae or pseudohyphae) or budding yeast. Vaginal secretion samples collected by swabs will be used for culture and for sequencing analysis of the vaginal microbiome (this sample will be taken in duplicates). If the patient is menstruating at this timepoint, the visit should be postponed until the menstruation is over, even though the visit will happen outside the visit window.

Procedures to be performed:

- Gynaecological examination by Investigator or authorised designee, evaluating vulvovaginal signs (erythema, oedema, and excoriation) and symptoms (itching, burning, and irritation) according to the scoring scale (0 to 3).
- Fungal saline microscopy assessment
- Vaginal swab for
 - Culture
 - Sequencing
- Vaginal self-swab for:
 - Sequencing
- Vaginal pH
- Recording of
 - Concomitant medications
 - AEs
 - Potential menstruation onset
- Product accountability – patients should be asked to return all used and not used treatment packages

Rescue treatment, according to standard clinical practice, will be offered if the intensity of the VVC symptoms is the same or higher compared to the inclusion visit (Visit 1, Day 0). See details in [Section 7.5.2](#).

An assessment of mycological cure will be done as soon as the results from the laboratory are received. A mycological cure is defined as no presence of *Candida* species. If the patient has both a clinical and mycological cure at Day 7, the Day 14 visit should be cancelled.

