5.4.5 Day 14 (± 2 days); Follow-up visit

Patients with clinically and mycologically cured VVC at Day 7, or patients initiating rescue treatment Day 7 (even if they are clinically cured according to the CIP), will not perform the Day 14-visit. For these patients, this visit will be omitted.

Patients without clinically and mycologically cured VVC at Day 7 will visit the clinic on Day 14 to have gynaecological examination performed. The Investigator or an authorised designee will assess the presence of vulvovaginal signs (erythema, oedema, and excoriation) and symptoms (itching, burning, and irritation) and score each sign and symptom on a scale of 0 to 3 (see [Section 9.1.2](#)).

Vaginal samples will be examined under a microscope for yeast forms (hyphae or pseudohyphae) or budding yeast. Vaginal secretion samples collected by swabs will be used for culture and for sequencing analysis of the vaginal microbiome. If the patient is menstruating at this timepoint, the visit should be postponed until menstruation is over.

The Investigator or delegatee will ask the patient about potential menstruation onset.

Procedures to be performed:

- Gynaecological examination by Investigator or authorised designee, evaluating vulvovaginal signs (erythema, oedema, and excoriation) and symptoms (itching, burning, and irritation) according to the scoring scale (0 to 3).
- Fungal microscopy assessment (KOH or saline preparation)
- Vaginal swab for
 - Culture
 - Sequencing
- Recording of:
 - Concomitant medications
 - AEs
 - Potential menstruation onset

Rescue treatment, according to standard clinical practice, will be offered if the intensity of VVC symptom is the same or higher compared to the inclusion visit (Visit 1, Day 0). See details in [Section 7.5.2](#).

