5.4.6 Day 25 (± 2 days); Follow-up visit

All patients will be contacted by the investigational site staff by telephone and asked about concomitant medications, AEs and potential menstruation onset. In addition, patients will be asked about symptom recurrence; “Have the symptoms recurred – yes/no?”. If the answer is “yes”, then the patient will be managed according to standard clinical practice. The site will decide if the patient should return to the site and if rescue medication should be prescribed (see [Section 7.5.2](#)).

Patients will also be reminded to complete the patient questionnaire for self-assessment of vulvovaginal symptoms, and to collect vaginal samples by self-swab. If the patient is menstruating at this time point, the patient should take the sample on the first day after menstruation. The self-swab samples will be sent by post to the laboratory for culture and sequencing of vaginal microbiome.

Procedures to be performed:

- Patient questionnaire (via mobile application)
 - Vulvovaginal symptoms of VVC (itching, burning, or irritation), evaluated by patients according to a scoring scale (0-3).
- Vaginal self-swab for
 - Culture
 - Sequencing
- Recording of:
 - Concomitant medications
 - AEs

- Potential menstruation onset

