12.2 Analysis data sets and populations

The full analysis set (FAS) is defined as all patients who received at least 1 treatment dose.

The per protocol analysis Set (PPAS) is a subset of the FAS and consists of patients who sufficiently complied with the CIP. Criteria for inclusion in the PPAS will be specified in the SAP.

All clinical performance analyses will be performed on both the FAS and the PPAS. The analyses performed on the FAS are to be considered as main and the analyses performed on the PPAS as supportive.

The safety analyses will be performed on the FAS.

12.3 Demographic, other baseline characteristics, prior and concomitant medications and compliance

The disposition of patients, demographic data and relevant baseline characteristics (including medical and surgical history and menstruation data), as well as prior and concomitant medication will be presented descriptively.

Medical history will be coded according to MedDRA and will be presented by system organ class (SOC) and preferred term (PT) as part of the baseline data.

Prior and concomitant medications will be coded using WHO ATC-index and summarised by ATC Class.

Treatment compliance data will be presented descriptively. For details on compliance assessment see [Section 7.6](#)

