3.3 Exploratory objective

The protocol did not state the objective for the exploratory endpoints, this has been added here.

To investigate if there is a difference in changes in the vaginal microbiome from baseline to day 7, 14, and 25 between patients that are clinical cured and patients that are not clinical cured and if presence of fungus DNA correlates with fungus assessed by culture and clinical cure.

To investigate *in vivo* duration as assessed by change in vaginal pH overall and separately in patients clinically cured and patients not clinically cured. A decrease in vaginal pH would indicate appropriate release duration.

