7.5 Demographics and Baseline Characteristics

Summary statistics and frequencies on demographic data (age, sex and ethnic origin) and consent details (childbearing potential, number of VVC infections during last 12 months) will be presented for the FAS.

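### Follow-up sampling is moved past menstruation but the Day 0 baseline is not, so a Day 0 to Day 7 fall in vaginal pH cannot be read cleanly as release duration

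*Protocol*

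**What the plan says.** Menstruation is treated as relevant to the disease: Protocol 3.1 states that "contraceptive pills, menstruation, and diabetes mellitus have been identified as predisposing factors for VVC".

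Each scheduled follow-up sampling has a menstruation rule:

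- Day 7 (Protocol 5.4.3): "If the patient is menstruating at this timepoint, the visit should be postponed until the menstruation is over", even if that takes the visit outside its window.
- Day 14 (Protocol 5.4.5): "If the patient is menstruating at this timepoint, the visit should be postponed until menstruation is over".
- Day 25 self-swab (Protocol 5.4.6): "If the patient is menstruating at this time point, the patient should take the sample on the first day after menstruation".

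At entry the only rule looks ahead. Protocol 5.4.1, repeated in 6.2, bars entry or defers it in one case: "the enrolment should be postponed, if menstruation is foreseen to occur at the time of the Day 7 visit". Nothing in the inclusion criteria (6.3), exclusion criteria (6.4) or restrictions (6.5) mentions bleeding on Day 0 or on the dosing days.

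Vaginal pH is measured on Day 0 and Day 7 only (Protocol 10.1.2, SAP 6.7). SAP 3.3 says of the change: "A decrease in vaginal pH would indicate appropriate release duration". SAP 7.9.5 repeats this more firmly, and Protocol 7.6 and 10.1.2 and SAP 6.7 take the same view.

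Onset and end of the last period are asked at Day 0, and later onset at each follow-up (Protocol 8.7). Protocol 12.3 promises to present "relevant baseline characteristics (including medical and surgical history and menstruation data"), whereas SAP 7.5 covers "Summary statistics and frequencies on demographic data (age, sex and ethnic origin) and consent details" and does not mention menstruation. SAP 7.10, which lists changes from the protocol, does not record the omission.

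**The concern.** A change from baseline is easiest to interpret when both measurements are taken under the same conditions. Here the follow-up value is kept clear of bleeding by rule and the baseline value is not. In a woman who is bleeding at Day 0, the Day 0 to Day 7 difference combines whatever the pessary does with whatever the end of a period does. There is no control arm in which the second part could be seen by itself.

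The pH change is given a specific meaning. It is the plan's measure of how long the product acts *in vivo*. Protocol 5.2 already used a smaller pH decrease among uncured women in the previous VVC study to argue that the device had not performed as intended. If the same reading is carried into this trial's report, a conclusion about the reformulated pessary could rest partly on cycle phase, and no planned table would let a reader check.

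**Working it through.** The plan gives no figure on this point, so there is none to reproduce. The check has two parts.

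**1. The rules side by side**

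| Time | pH measured | Menstruation rule |
|---|---|---|
| Day 0 | yes | none for Day 0 itself; entry deferred only if bleeding is foreseen at Day 7 |
| Days 0–5 (dosing) | no | none |
| Day 7 | yes | visit postponed until bleeding is over |
| Day 14 | no | visit postponed until bleeding is over |
| Day 25 | no | self-swab moved to after bleeding |
| Early withdrawal | no | none (Protocol 5.4.7) |

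SAP 7.1.2 takes the last non-missing value before first administration as baseline, which for pH is the Day 0 visit. The entry rule does not protect it: a period of up to 7 days that is in progress on Day 0 is over by Day 7, so such a woman may be enrolled.

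**2. How many women could be affected**

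Inputs from the documents: the Day 7 entry rule, the Day 7 window of +2 days, and 26 planned patients. Assumptions not in the documents: cycle length C of 24 to 32 days, period length M of 3 to 7 days, and Day 0 falling at random in the cycle. Let w = 0 if entry is deferred for bleeding on Day 7 only, and w = 2 if deferred for bleeding on any of Days 7 to 9.

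Permitted cycle days for Day 0: C − M − w.

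Share bleeding on Day 0: M / (C − M − w), because for M up to 7 no woman bleeding on Day 0 is removed by the entry rule.

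- Lowest (C = 32, M = 3, w = 0): 3/29 = 10%, and 26 × 3/29 = 2.7 women.
- Middle (C = 28, M = 5, w = 0): 5/23 = 22%, or 5.7 women.
- Highest (C = 24, M = 7, w = 2): 7/15 = 47%, or 12.1 women.

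Share bleeding on at least one of Days 0–5: M + 5 cycle days give this, and the entry rule removes M − 2 of them. That leaves M + 5 − (M − 2) = 7, so the share is 7 / (C − M − w).

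- Lowest: 7/29 = 24%, or 6.3 women.
- Middle: 7/23 = 30%, or 7.9 women.
- Highest: 7/15 = 47%, or 12.1 women.

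The Day 0 shares are probably too high, since inclusion criterion 3 requires a white or creamy discharge, which makes heavy flow at Day 0 unlikely. Women without regular bleeding would lower both shares. Presentation at random is also a simplification, given that Protocol 3.1 names menstruation as a predisposing factor.

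The size of a menstrual effect on pH cannot be computed. Protocol 3.1 links changes in flora to a higher pH in general terms, but no section says what bleeding does to pH.

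**The case against.** The strongest reply is that the mechanism is not in the documents. They call menstruation a predisposing factor for the infection; they do not say that it raises pH, shifts flora or alters symptom scores. This stands, and it limits the point to an ambiguity in the reading rather than a demonstrated bias. Direction is also open: if bleeding did raise pH, a period that starts after Day 0 and ends just before the Day 7 visit could work against a fall.

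The reply can add that pH is exploratory, is summarised descriptively and is also shown by cure status. A shift common to cured and uncured women would tend to cancel in that comparison. This is fair, but the release-duration reading attaches to the pH decrease itself, not only to the contrast.

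A reader might infer more than the text supports:

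- **That the primary cure rate is biased.** Clinical cure is a CVVS threshold at Day 7–14, not a change from Day 0, and those visits are already moved past menstruation. The plan defers examinations and samples; it nowhere calls dosing during bleeding unsuitable. Protocol 3.3.2 suggests that limited vaginal discharge may have hindered dissolution of the previous formulation, but it draws no conclusion about menstrual flow.
- **That planned microbiome change tables are affected.** SAP 7.9.5 leaves the bacterial endpoint to others and summarises fungal DNA by timepoint. It contains no sequencing change-from-Day-0 table to correct.
- **That every post-baseline sample is protected.** The early-withdrawal swab has no menstruation rule.

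**Conclusion.** The asymmetry is in the text and no section closes it. Day 0 pH can be taken during bleeding, Day 7 pH is not, and the SAP interprets the difference as a property of the product without a control arm or any use of the menstruation dates. The reading may therefore partly reflect cycle phase, by an amount and in a direction that the documents do not give.

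Under the stated assumptions about 10% to 47% of women (3 to 12 of 26) would bleed on Day 0, probably fewer because of the discharge criterion. These figures describe how many women could be affected, not the size of any bias.

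The consequence is confined to an exploratory reading and a missing baseline summary; the primary analysis and the sample size are untouched. This is a minor, optional improvement, worth making because it needs no new data. It is best settled before the pH results are examined.

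**What to change.** 1. In SAP section 8, derive a flag for bleeding at the Day 0 visit from the recorded onset and end dates. State how a period still in progress at Day 0 is identified, since the question concerns the last period and its end date may be blank.
2. In SAP 7.9.5, present the Day 0 to Day 7 pH change for women not bleeding at Day 0 beside the all-women table. Base any statement about release duration on the former, and word it as consistent with release rather than as showing it.
3. In SAP 7.5, restore the menstruation data promised in Protocol 12.3, or list the omission in SAP 7.10.
4. Reconcile Protocol 5.4.1 and 6.2 with 5.4.3 to 5.4.6 on sampling during menstruation.

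A cure rate excluding women who bled on any of Days 0–5 is optional and should be descriptive only. On the assumptions above it could remove about 6 to 12 of 26 women, leaving 14 to 20.

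The cost is a short SAP revision, one derived flag and one additional table. The downside is fewer women in that one exploratory pH table.
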